## 16.2. SECONDARY EFFICACY

### 16.2.1. SECONDARY EFFICACY VARIABLES & DERIVATIONS

#### 16.2.1.1. Percent Reduction in Daily CS (Prednisone or Equivalent) Dose from Baseline to Week 39

Percent reduction in daily CS (prednisone or equivalent) dose is defined in Section 16.1.1.

#### 16.2.1.2. Time to First Episode of MG Worsening from Baseline through Week 39

MG worsening is defined in Section 3.3.3 of the protocol as at least a 4-point increase in QMG total score from Baseline. Time to first episode of MG worsening from baseline through Week 39 is calculated as the date of the first QMG assessment meeting the MG worsening criterion – date of baseline visit + 1. Subjects who never experience MG worsening through Week 39 will be censored at the date of their last non-missing QMG total score assessment on or prior to the date of visit for Week 39.

### 16.2.2. MISSING DATA METHODS FOR SECONDARY EFFICACY VARIABLE(S)

#### 16.2.2.1. Missing Data Method for Percent Reduction in Daily CS Dose at Week 39

For subjects who discontinued the study early with adverse outcomes related to MG, the missing percent reduction in CS dose at Week 39 will be imputed using the WOCF method. For subjects who have missing CS dose reduction at Week 39 due to other reasons, the missing CS dose will be imputed using the LOCF approach for continuous endpoints as detailed in Section 7.3.

Missing data will also be handled with the OC approach, where the analysis will be based on observed non-missing data only and subjects with missing data at Week 39 will be excluded from the analysis.

#### 16.2.2.2. Missing Data Method for Time to First Episode of MG Worsening

Subjects with no post-baseline data will be censored at the date of Week 0 visit (i.e., at Day 1). Subjects with missing data for at least one but not all scheduled visits will be censored at the last visit with non-missing data on or prior to the date of visit for Week 39, unless they experience the event based on the assessments available. Both scheduled and unscheduled visits are considered in identifying the last visit with non-missing data.

Document: CCI

Author: PPD

Version Number:

Version Date:

Final 2.0  
12Apr2019

Template No: CCI

Effective Date: 01Apr2016

Reference: CCI

Copyright © 2009, 2010, 2012, 2016 CCI. All rights reserved.

The contents of this document are confidential and proprietary to CCI. Unauthorized use, disclosure or reproduction is strictly prohibited.

### 16.2.3. ANALYSIS OF SECONDARY EFFICACY VARIABLES

The secondary efficacy analyses will be performed for the mITT population.

#### 16.2.3.1. Analysis of Percent Reduction in Daily CS Dose at Week 39

The percent daily CS dose reduction from baseline at Week 39 will be analyzed using analysis of covariance (ANCOVA; Dobson, 2002). The ANCOVA model will include the percent daily CS dose reduction as dependent variable, treatment as fixed effect, and baseline daily CS dose as a covariate.

#### 16.2.3.2. Analysis of Time to First Episode of MG Worsening

For the endpoint of time to first episode of MG worsening, Kaplan-Meier estimates (Kaplan, 1958) will be provided for each treatment group. The probability of first episode of MG worsening at each scheduled visit will be calculated. The treatment comparison will be performed using a log-rank test adjusted for baseline CS dose level (15 to 40 mg versus 41 to 60 mg).

## 16.3. EXPLORATORY EFFICACY

### 16.3.1. EXPLORATORY EFFICACY VARIABLES & DERIVATIONS

#### 16.3.1.1. Percent of Subjects Achieving a 75% or Greater Reduction in CS Dose (Prednisone or Equivalent) at Week 39 from Baseline

This endpoint will be derived in the same way as the primary endpoint described in Section 16.1.1.

#### 16.3.1.2. Percent of Subjects CS-free at Week 39

Subjects whose daily CS dose prescribed at Week 39 is 0 mg will be considered CS-free.

#### 16.3.1.3. Percent of Subjects Achieving a Dose of CS of Less than or Equal to 7.5 mg per Day of Prednisone (or Equivalent) at Week 39

The percent of subjects whose daily CS dose prescribed at Week 39 is less or equal to 7.5 mg will be analyzed.

#### 16.3.1.4. CFB in Fasting Serum Glucose (mg/dL) at Week 39

The CFB is calculated as indicated in section 6.7.

#### 16.3.1.5. Percent of Subjects with Fasting Glucose Less than or Equal to 125 mg/dL at Week 39

The percent of subjects with fasting glucose less than or equal to 125mg/dL at Week 39 will be

Document:

CCI

Author:

PPD

Version Number:

Final 2.0

Version Date:

12Apr2019

Template No: CCI

Reference: CCI

Effective Date: 01Apr2016

Copyright © 2009, 2010, 2012, 2016 CCI. All rights reserved.

The contents of this document are confidential and proprietary to CCI. Unauthorized use, disclosure or reproduction is strictly prohibited.

calculated.

#### 16.3.1.6. Percent of Subjects Experiencing MC or Episode of MG Worsening Requiring Inpatient Care from Baseline through Week 39

Subjects who experience MC or Episode of MG worsening requiring inpatient care from baseline to Week 39 will be those who had at least one adverse event (AE) that met ALL criteria below:

- The preferred term (PT) of the AE is either “Myasthenia gravis crisis” or “Myasthenia gravis”
- The AE is serious, with the reason for seriousness being “Required/Prolonged Hospitalization”
- The onset date/time of the AE is on or after the start date/time of the first infusion of study medication, i.e., the AE is treatment-emergent
- If the subject completed the Week 39 visit, the onset date of the AE is on or prior to the date of visit for Week 39

#### 16.3.1.7. Percent of Subjects Experiencing MC or Episode of MG Worsening Requiring Inpatient Care from Week 39 to Week 45

This endpoint will be derived in the same way as the endpoint described in Section 16.3.1.6. Subjects who experience MC or Episode of MG worsening requiring inpatient care from Week 39 to Week 45 will be those who completed Week 39 visit and had at least one adverse event (AE) that met ALL criteria below:

- The preferred term (PT) of the AE is either “Myasthenia gravis crisis” or “Myasthenia gravis”
- The AE is serious, with the reason for seriousness being “Required/Prolonged Hospitalization”
- The onset date of the AE is after the date of visit for Week 39

#### 16.3.1.8. Percent of Subjects with 0, 1, or 2 Episodes of MG Worsening from Baseline to Week 39

The number of episodes of MG worsening is defined as the number of QMG assessments where at least a 4-point increase in QMG total score from Baseline is observed. This includes assessments at scheduled, unscheduled or early termination visits on or prior to the subject reaching the Week 39 visit.

#### 16.3.1.9. CFB in MG-QOL 15 at Week 39 and Week 45

The MG-QOL 15 is made up of 15-items. All individual items related to degree of disease-related impairment are rated on a Likert scale ranging from “not at all” (score 0 points) to “very much” (score 4 points), with higher scores indicating worse disease. The results of the MG-QOL 15 items are entered on the eCRF. The MG-QOL 15 is shown in Appendix 6.

Document:

CCI

Author:

PPD

Version Number:

Final 2.0

Version Date:

12Apr2019

Template No:

CCI

Reference:

CCI

Effective Date: 01Apr2016

Copyright © 2009, 2010, 2012, 2016 CCI All rights reserved.

The contents of this document are confidential and proprietary to CCI. Unauthorized use, disclosure or reproduction is strictly prohibited.

---

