A schematic of the overall study design and essential activities is shown in Figure 3-1, and a schedule of study procedures is provided in Appendix 1. Tools for assessing MG are provided in Appendix 2, Appendix 3, Appendix 4, Appendix 5, Appendix 6, and specific safety monitoring in Appendix 7, Appendix 8, and Appendix 9.

Worsening of MG symptoms

If at any point during the CS Tapering phase, the subject suffers a worsening of his/her MG symptoms, as defined in Section 3.3.3 "Definition and Management of MG Worsening," the CS dose will be increased by 20 mg if the CS dose (mg/day) at which worsening occurs is ≥15 mg/day or the dose will be increased by 15 mg/day if the CS dose (mg/day) at which worsening occurs is <15 mg/day in accordance with Table 3-3 and Table 3-4. The increased CS dose (prednisone equivalent) will be assessed over the next 2 consecutive visits (6 weeks). The subject's symptoms of MG must have re-stabilized while receiving this higher dose of CS for the subject to continue in the study. Stabilization is defined as a Quantitative Myasthenia Gravis (QMG) score increase of ≤3 points relative to Baseline/Week 0 and a return to baseline of clinical symptom(s) that triggered the definition of worsening of MG as judged by the physician investigator. If the episode of MG worsening fails to improve with the above CS dose increase within 6 weeks (by the second subsequent visit), the subject will be withdrawn from the study.

If the increased CS dose was successful in abating the QMG score worsening to within ≤3 points relative to Baseline/Week 0 and a return to baseline of clinical symptom(s) that triggered the definition of MG worsening as judged by the physician investigator, then a second attempt at tapering of the subject's new CS dose will be initiated according to Section 3.3.4. On this second attempt to taper, the CS dose will be reduced in the same fashion as outlined above; however, the dose will not decrease below the last dose at which the subject was stable prior to their episode of MG worsening. If the subject requires a second CS dose increase at any time, the subject will be withdrawn from the study. Also see Early Discontinuation Visit (Section 3.8.2.6) and Section 3.11.

Protocol GTI1306 - Amendment 2

IP = Investigational product, CS = Corticosteroid

Figure 3-1 Overall Study Schema

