3.3.3 Definition and Management of MG Worsening

During the study, MG worsening will be defined as:

• QMG score increase by ≥ 4 points relative to Baseline/Week 0

During the CS Tapering phase, if a subject meets the definition of MG worsening as defined above, then the following increase in CS dose will occur as shown in Table 3-3 and Table 3-4:

Table 3-3 *Daily* CS Dose Increase in Response to Worsening MG (CS Tapering Phase Only) (prednisone equivalent)

CS Dose (mg/day) at Which Worsening Occurs	Dose Increase (mg/day)
≥ 15	20
< 15	15

Table 3-4 Every Other Day CS Dose Increase in Response to Worsening MG (CS Tapering Phase Only) (prednisone equivalent)

Every Other Day CS Dose (mg/every other day) at Which Worsening Occurs	Every Other Day Dose Increase (mg/every other day)
≥ 30	40
< 30	30

If an episode of MG worsening fails to improve with the above CS dose increase within 6 weeks (by the second subsequent visit), or if another specific episode requires a second dose increase at any time, the subject will be withdrawn from the study. Also see Early Discontinuation Visit (Section 3.8.2.6 and Section 3.11).

Special Note for subjects tapered to 0 mg CS per day: Some subjects with MG are uniquely sensitive to complete CS withdrawal (0 mg prednisone equivalent daily), and may become more vulnerable to MG triggers and sudden MG exacerbations. Therefore if a subject has tapered to 0 mg prednisone equivalent daily, any worsening MG signs or symptoms must be evaluated in clinic as soon as possible (recommended within 24 hours, allowed up to 48 hours) and treated aggressively with CS dose increase as delineated in the tables above. Once tapered to 0 mg CS per day, a 4-point QMG increase from Baseline/

Week 0 is not required for re-initiating CS because deterioration can be of greater severity and speed than expected and may be difficult to reverse.

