5.1.3.3 Exploratory Efficacy Analyses

Exploratory efficacy analyses will be based on the ITT population. The following exploratory efficacy variables will be analyzed with the same approach as the primary efficacy endpoint using the ITT population: In the situation where the CMH method is not appropriate due to the sparse events, the Fisher exact test will be used for treatment comparison.

Exploratory efficacy variables that will be evaluated in this study include the following:

- Percent of subjects achieving a 75% or greater reduction in CS dose (prednisone or equivalent) at Week 39 (Visit 14) from Baseline/Week 0 (Visit 1)
- Percent of subjects CS-free at Week 39 (Visit 14)
- Percent of subjects achieving a dose of CS of less than or equal to 7.5 mg per day of prednisone (or equivalent) at Week 39 (Visit 14)
- Percent of subjects with fasting glucose less than or equal to 125 mg/dL at Week 39 (Visit 14)
- Percent of subjects experiencing MC (as defined in Section 3.3.5) or episode of MG worsening requiring inpatient care from Baseline/Week 0 (Visit 1) through Week 39 (Visit 14)
- Percent of subjects experiencing MC or episode of MG worsening requiring inpatient care from Week 39 to Week 45 (at Visit 14 and Visit 16)
- Percent of subjects with 0, 1, or 2 episodes of MG worsening from Baseline/Week 0 to Week 39 (Visit 1 to Visit 14) (in aggregate and by number of episodes/subject).

The following exploratory endpoints will be analyzed using the ANCOVA with treatment as main factor and baseline CS dose as covariate. In addition, the mixed model for repeated measurement (MMRM) will also be performed.

- Change from Baseline/Week 0 in fasting serum glucose at Week 39 (Visit 14)
- Change in 15-Item MG-QOL 15 from Baseline/Week 0 to Week 39 (Visit 1 to Visit 14), and from Baseline to Week 42 and Week 45 (Visit 15 and Visit 16)
- Change in MG-ADL from Baseline/Week 0 to Week 39 (Visit 14), and from Baseline to Week 42 and Week 45 (Visit 15 and Visit 16)
- Change from baseline in serum IgG trough at Week 9 (Visit 4), Week 24 (Visit 9), and Week 39 (Visit 14)
- Change from baseline in binding, blocking, and modulating AChR antibodies at Week 39 (Visit 14)
- Change from baseline in HbA1c at Week 39 (Visit 14)

In addition, exploratory analyses of the correlation between CS dose reduction and blood pressure (hypertension), measures of glycemic control, weight, body habitus/Cushingoid features, and mood/emotional well-being will be explored.

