### 7.3. MISSING DATA

Imputation for missing values will be applied to continuous efficacy endpoints using the LOCF or the WOCF method.

Primary efficacy endpoint of CS dose:

For the primary efficacy endpoint of CS dose, the WOCF method will be applied to subjects who discontinued early from the study with adverse outcomes related to MG, defined as those subjects who met ALL criteria below:

- The primary reason for discontinuation is one of the following: “Adverse Event”, “Death”, “Discontinuation due to MG crisis requiring hospitalization”, or “MG worsening (CS-unresponsive or 2nd episode)”
- The subject had at least one adverse event (AE) with preferred term (PT) of either “Myasthenia gravis crisis” or “Myasthenia gravis”
- The AE is serious, with the reason for seriousness being “Required/Prolonged Hospitalization” or “Resulted in Death”
- The onset date/time of the AE is on or after the start date/time of the first infusion of study medication, i.e., the AE is treatment-emergent

For these subjects, the worst values, i.e., the highest average daily CS dose available among all eligible visits [including the Baseline visit, all post-baseline scheduled visits, and the Early Termination visit(s)], will be carried forward to impute the missing CS dose for all remaining visits.

For subjects who discontinued the study early due to any other reasons, the LOCF method will be used to impute the missing values, i.e., the last non-missing post-baseline CS dose value available among all eligible visits [including all post-baseline scheduled visits and the Early Termination visit(s)] will be carried forward to impute missing values for all remaining visits.

Note for the primary efficacy endpoint of CS dose, the values to be considered as candidates for carrying forward are the derived average daily CS dose at the relevant scheduled visits, incorporating potential changes in the prescribed CS dose within the prior 3 weeks (see section 16.1.1 for derivation details).

Other continuous efficacy variables:

For all other continuous efficacy variables and for all subjects who discontinued the study early, regardless of the reason, the LOCF method will be used to impute the missing values, i.e., the last non-missing post-baseline value (including scheduled, unscheduled, and early termination) will be carried forward to impute missing values for all remaining visits.

All continuous efficacy variables:

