## Analysis Plan

- Percent of subjects with fasting glucose less than or equal to 125 mg/dL at Week 39
- Percent of subjects experiencing MC or episode of MG worsening requiring inpatient care from baseline through Week 39
- Percent of subjects experiencing MC or episode of MG worsening requiring inpatient care from Week 39 to Week 45
- Percent of subjects with 0, 1, or 2 episodes of MG worsening from baseline to Week 39

In the case of sparse events, where at least one of the frequencies is less than 5 in a given cell (i.e., a unique combination of baseline CS dose level, treatment, and the binary response), both unstratified and stratified analyses will be performed using exact methods. For the unstratified analysis, the Fisher's exact test (Agresti, 1992) will be used for treatment comparison. The odds ratio and the exact 95% confidence interval will also be calculated overall and separately for each stratified baseline CS dose level (15-40 mg/day versus 41-60 mg/day). For the stratified analysis, the Zelen's exact test will be used to test homogeneity of odds ratios. The CMH common odds ratio and its exact 95% confidence interval will also be calculated. Finally, an exact test will be used to test the hypothesis of the common odds ratio being 1.

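### SAP 16.3.1.8 counts QMG assessments rather than episodes, so one persistent MG worsening can be reported as 2, 3 or more episodes

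*SAP*

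**What the plan says.** The protocol lists the number of episodes of MG worsening from Baseline to Week 39 as an exploratory objective (2.1.3). Section 5.1.3.3 plans to report the percent of subjects with 0, 1 or 2 episodes, "in aggregate and by number of episodes/subject". SAP 16.3.3.1 keeps the same categories: "Percent of subjects with 0, 1, or 2 episodes of MG worsening from baseline to Week 39".

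The counting rule is in SAP 16.3.1.8: "The number of episodes of MG worsening is defined as the number of QMG assessments where at least a 4-point increase" over the Baseline total is seen. It continues: "This includes assessments at scheduled, unscheduled or early termination visits on or prior to the subject reaching the Week 39 visit". No recovery is required between two counted assessments.

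The protocol gives no formal definition of an episode, but its management rules use the word consistently:

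- Section 3.1 has the increased CS dose assessed over the two visits (6 weeks) after a worsening. It gives a test for the end of that state: "Stabilization is defined as a Quantitative Myasthenia Gravis (QMG) score increase of ≤3 points relative to Baseline/Week 0", together with return of the triggering symptoms to baseline.
- Section 3.3.3 deals with an episode that fails to improve by the second subsequent visit, and separately with a further one: "if another specific episode requires a second dose increase at any time, the subject will be withdrawn from the study".
- SAP 7.3 likewise names, within one discontinuation reason, worsening that does not respond to CS and a second episode as two different situations.

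**The concern.** The variable is labelled as a number of episodes but is computed as a number of elevated readings. A subject with one worsening that does not settle is measured again at the next visits, and each of those readings adds an episode. A count of 2 then cannot tell one two-visit episode from two separate episodes. A subject with one long episode can appear worse than a subject with two short ones.

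At stake is the split among subjects who worsened at least once. It would partly reflect how often QMG was measured while they were worse. Measurement frequency need not be equal between arms. Protocol 3.3.3 asks for prompt clinic evaluation of any worsening in subjects tapered to 0 mg, which may add unscheduled QMG assessments in whichever arm reaches 0 mg more often.

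**Working it through.** The documents give no figure to reproduce here, so the check applies the SAP rule to the visit schedule.

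**Inputs**

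- QMG is scheduled every 3 weeks (protocol Appendix 1). Post-baseline assessments through Week 39: 39 / 3 = 13.
- Worsening threshold: +4 or more from Baseline (protocol 3.3.3).
- An unresolved taper-phase episode covers the trigger visit and the next two visits (protocol 3.1 and 3.3.3): 1 + 2 = 3 scheduled assessments.
- Counting stops at Week 39 (SAP 16.3.1.8).
- The ET visit includes QMG (protocol 3.8.2.6).

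**Rules compared**

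- SAP count = number of assessments with change of 4 or more.
- Run count = number of unbroken runs of such assessments.

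**One unresolved episode that stays at +4 or more (run count is 1 in every row)**

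| Onset | Elevated scheduled visits up to Week 39 | SAP count | SAP count with one separate ET assessment before Week 39 |
|---|---|---|---|
| Weeks 9 to 30 (8 visits) | onset, +3 weeks, +6 weeks | 3 | 3 + 1 = 4 |
| Week 33 | 33, 36, 39 | 3 | 3 (second follow-up visit is already Week 39) |
| Week 36 | 36, 39 | 2 | not applicable |
| Week 39 | 39 | 1 | not applicable |

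So all 9 possible onset visits from Week 9 to Week 33 give 3 or more.

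**Example sequences of QMG change from Baseline**

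| Sequence | SAP count | Run count |
|---|---|---|
| 0, 5, 5, 5 | 3 | 1 |
| 0, 5, 5, 2, 2 | 2 | 1 |
| 0, 5, 2, 2 | 1 | 1 |
| 0, 5, 2, 2, 5 | 2 | 2 |
| 4, 3, 4 | 2 | 2 |

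The first and fourth rows give the reversal: one episode scores 3 and two episodes score 2. The second and fourth rows both score 2 for different histories. An episode that has resolved by the first follow-up visit is counted correctly.

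**Share affected.** A single-episode subject is miscounted exactly when QMG is still +4 or more at a second counted assessment. The misclassified share therefore equals the share with such persistence, which could lie anywhere from 0 to 100%. The documents give no value for it.

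**Correction elsewhere.** No other section repairs the rule. SAP 16.2.1.2 uses only the first qualifying assessment, SAP 16.3.2.1 only rules out imputation, and SAP 16.3.3.1 only repeats the categories. SAP 3.3 declares the move to the mITT population and nothing about this count.

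**The case against.** The SAP rule is explicit and reproducible. Because the protocol defines worsening only as a 4-point rise and leaves data handling to the SAP, the rule can be read as filling a gap. That weakens any charge of an undeclared change: the bare fact that SAP 3.3 is silent stands, but no stated protocol counting rule was replaced. It does not make the count measure what its label says.

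The protocol's wording also varies. Section 3.3.3 speaks of another specific episode needing a second dose increase, while 3.8.2.5 speaks of the specific episode needing one. The two passages should be reconciled, but both treat an episode as something that persists.

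The output templates are not available for review, so a row for 3 or more may exist there. The point is therefore limited to the SAP text.

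A run rule is itself a QMG-only proxy. It ignores clinical symptoms. It ends an episode on one reading of +3 or less, whereas protocol 3.3.4 asks for stabilisation over at least two visits before a second taper. It scores +4, +3, +4 as 2. Neither rule captures worsening at 0 mg that is treated without a 4-point rise. These limits stand and should be stated, but the run rule does remove the repeat counting of one unbroken elevation.

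The table above leaves out onset at Weeks 3 and 6 and the second ET visit that SAP 6.4 allows. Both omissions understate the possible count.

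**Conclusion.** The concern holds as stated, at minor severity. As written, the rule gives 3 for one unresolved episode with taper-phase onset by Week 33, and 2 for two distinct one-visit episodes. This assumes that QMG stays at +4 or more, that no QMG total is missing and that the subject is not withdrawn earlier, for example for crisis.

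The number of subjects affected cannot be estimated from the documents, so repeat counting is shown to be possible but not shown to be material.

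The effect is confined to the split by number of episodes among subjects with at least one. The percent with none, the time to first worsening and the primary endpoint do not use the count. SAP 16.3.3 treats exploratory p-values as informative only, and SAP 7.4 describes a Phase 2 proof-of-concept study without multiplicity adjustment.

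**What to change.** In SAP 16.3.1.8:

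- Define an episode as a run of QMG assessments at +4 or more from Baseline, ending on return to +3 or less. A new episode requires a new rise to +4 or more. Unscheduled and ET assessments within a run do not add to the count.
- State that +3 or less is only the QMG part of the protocol's stabilisation definition, that the symptom part is not used, and that +4, +3, +4 therefore counts as 2.
- Add a category for 3 or more, unless the templates already have one. Two is not a strict maximum, because the dose-increase tables tied to the withdrawal rule apply in the taper phase only.

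If a count of assessments is really intended, rename the variable as the number of assessments with MG worsening and list it in SAP 3.3.

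The cost is SAP wording, one extra table category and a small programming change. QMG data already collected are sufficient.
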